Cover Page

The impact of Therapeutic Exercises on the Quality of Life and Shoulder Range of Motion in
Women after a Mastectomy, a RCT.

June 30, 2018

Submitted November 27, 2019

Protocol: The Institution Review Board (IRB) of the university and the medical center granted approval for the study. Seventy-six women were approached while waiting for their surgery after approval from their surgeon. Women who showed interest in participating signed a consent form and were then randomly assigned to one of two groups by flipping a coin. Thirty women ended up in the intervention group and 30 in the control group. Figure one details the protocol of the study. The intervention group received pre-surgery education and training on therapeutic exercises in addition to the routine hospital care. The control group, which had 30 patients, received the routine hospital care that did not include any exercise training or education. Routine hospital care included explanation by the surgeon on the surgical procedure with follow up at two and four weeks after discharge. The educational material was developed by the principal investigator (PI) and included a power point and a booklet with instructions on the exercises as well as information about the surgery and what to expect after the surgery. The educational material was based on previous research and adopted to our population after consultation with a panel of experts including two nurses and three physicians. Eligible women were approached while waiting for their appointment with their surgeon. If they showed interest in participating they signed a consent form. The PI explained the study and what is involved in participating including the weekly phone calls for women in the intervention group. Participants were told that they will be visited at home by the PI to assess their ROM and to fill out a questionnaire.

The intervention: The intervention consisted of three phases. Phase 1 took place the day prior to surgery at which time the intervention and control, groups completed the QoL-BC survey and shoulder ROM was measured using the goniometer. Phase 2 consisted of one to one education with the intervention group prior to surgery. Education consisted of a power point presentation regarding the therapeutic exercises, information about the surgery and a booklet with pictures of the exercises to take home. In this phase demonstration of the exercises by the researcher with a return demonstration by the patient was done to ensure proper techniques. The researcher called the patients at home every week to ensure that the women were continuing the exercises. Phase 3 was conducted for both groups in the patient's homes and entailed reassessment of shoulder ROM and completing the QoL-BC at the second and fourth week after discharge. All patients completed the study. The exercises included deep breathing as well as shoulder exercises such as extension of the triceps, biceps curl, paddling in sitting position, fluttering with both arms, hands behind neck, forward wall crawls, and side wall crawls.

Patients were instructed to perform 10 repetitions of each exercise during hospitalization, with further guidance at the outpatient follow-up appointment. Shoulder flexion was limited to 90° of active assisted

ROM for the first few days post-surgery and until the drains were removed, then gradually increased after the third postoperative day. Patients were instructed to keep performing the exercises after discharge.

Results

Patient characteristics

There were no differences between groups at baseline. The majority of the patients in both groups were between 35 and 42 years of age, roughly 70% were married, and the majority of patients had a high school or higher education.

Shoulder range of motion scores: While the shoulder ROM scores were not significantly different between groups prior to surgery, there were significant differences at the second and fourth weeks after surgery (Table 2). Flexion at two weeks for the intervention group was 133.80 ± 6.79 and for the control group it was 131.17 ± 2.20 , $p = 0.001$, at four weeks it was 167.97 ± 4.09 for the intervention group and 159.92 ± 1.73 for the control group, $p < 0.001$. Extension significantly improved for the study group at two weeks with a mean of 42.77 ± 2.30 versus 38.73 ± 1.46 , $p < 0.001$ and at four weeks 53.07 ± 2.12 versus 49.03 ± 1.25 , $p < 0.001$. Additionally, abduction demonstrated a significant difference between the study and control groups at two weeks 143.50 ± 4.42 versus 138.57 ± 1.78 , $p < 0.001$ and at four weeks 167.03 ± 4.61 versus 159.40 ± 1.69 , $p < 0.001$.

Differences between groups on each of the QoL-BC 4 subscales: There were no significant differences between groups at baseline on the QoL survey with both groups having low QoL scores. However, there were significant differences between groups at two and four weeks after surgery on the four subscales (Table 3). Physical well-being was significantly improved with the study group experiencing higher level of physical well-being than the control group; at two weeks, 58.37 ± 6.16 versus 50.23 ± 7.78 , $p = 0.001$, and at four weeks 66.67 ± 6.19 versus 54.97 ± 9.55 , $p < 0.001$. For Psychological well-being there was significant difference between the two groups at two weeks, the study group mean 142.33 ± 15.48 and the control group 122.93 ± 7.34 , $p < 0.001$, and at four weeks, 169.50 ± 26.43 and 145.67 ± 12.44 , $p < 0.001$. Social well-being at two weeks was significantly higher for the study group 43.57 ± 7.045 versus 29.30 ± 8.30 for the control group, $p < 0.001$; and at four weeks 54.33 ± 8.73 for the study group versus 42.33 ± 5.08 for the control group, $p < 0.001$. Spiritual well-being was significantly improved at two weeks, with a mean for the study group of 51.07 ± 4.37 versus 44.90 ± 6.05 , $p < 0.001$; and at four weeks 56.33 ± 3.96 versus 48.93 ± 2.61 , $p < 0.001$.

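### Does the lack of any described masking of the home range-of-motion assessor call for a change to the plan?

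*Combined protocol and SAP*

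**What the plan says.** The Protocol section says of the follow-up visits: "Participants were told that they will be visited at home by the PI to assess their ROM and to fill out a questionnaire". It also gives the PI a part in the intervention: "The educational material was developed by the principal investigator (PI)".

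The section on the intervention uses another label for the person who delivered it. On teaching it says "In this phase demonstration of the exercises by the researcher with a return demonstration by the patient was done", and on the telephone contact "The researcher called the patients at home every week to ensure that the women were continuing the exercises". It does not say whether this researcher is the PI.

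Phase 3, carried out at home in both arms, "entailed reassessment of shoulder ROM and completing the QoL-BC at the second and fourth week after discharge". No assessor is named there, and nothing is said for or against masking. The Protocol section adds that "Figure one details the protocol of the study"; that figure is not reproduced in the text available. The study is already finished: "All patients completed the study".

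**The concern.** A goniometer angle depends on how the observer places the instrument and judges the end of the movement. An assessor who knows which women were trained, and who wrote the training material, could read slightly higher in that arm without intending to. Randomisation does not protect against this, because the error enters at measurement. Similar ROM before surgery does not rule it out at follow-up. Women cannot be masked to exercise training, so masking the reader is the safeguard one would look for, and the text does not mention it.

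At stake are the six between-arm ROM comparisons at two and four weeks. A systematic shift would be counted as an exercise effect. The QoL-BC is affected less: women who know their arm complete it themselves, and masking the visitor would not cure that.

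**Working it through.** **What the text establishes.** Four statements would be needed to show a flawed design.

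| Statement | Status in the text |
|---|---|
| The PI was the announced home assessor | Stated (Protocol) |
| The PI was also the researcher who taught and telephoned | Not stated |
| The home assessor knew each woman's group | Not stated |
| No masking step existed | Not stated; the protocol figure cannot be seen |

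Only the first is documented. What is supported is that masking is not described; that it was absent is not shown.

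**How large a bias would matter.** Inputs are the means and ± values under the heading on shoulder range of motion scores, and 30 women per arm from the Protocol section. The ± values carry no label, so reading them as SDs is an assumption. The printed p-values support it. If they were standard errors, two-week extension would give t = 4.04 / √(2.30² + 1.46²) = 4.04 / 2.72 = 1.48, which cannot yield the printed p < 0.001.

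For each comparison, D is the difference in means (intervention minus control) and SE = √(s₁²/30 + s₂²/30). The Welch degrees of freedom give the critical value t*. If every reading in the trained arm were too high by a constant amount, two-sided significance at 5% would be lost once that amount reached the lower 95% limit, D − t* × SE.

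Example, two-week extension: D = 42.77 − 38.73 = 4.04; SE = √(2.30²/30 + 1.46²/30) = 0.497; df = 49.1; t* = 2.009. Then 4.04 − 2.009 × 0.497 = 3.04°, and 3.04 / 4.04 = 75% of the difference.

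| Result | D (°) | SE | Welch df | t* | Shift that removes significance (°) | Share of D |
|---|---|---|---|---|---|---|
| Flexion, week 2 | 2.63 | 1.303 | 35.0 | 2.030 | −0.02 | about 0% |
| Flexion, week 4 | 8.05 | 0.811 | 39.1 | 2.023 | 6.41 | 80% |
| Extension, week 2 | 4.04 | 0.497 | 49.1 | 2.009 | 3.04 | 75% |
| Extension, week 4 | 4.04 | 0.449 | 47.0 | 2.012 | 3.14 | 78% |
| Abduction, week 2 | 4.93 | 0.870 | 38.2 | 2.024 | 3.17 | 64% |
| Abduction, week 4 | 7.63 | 0.896 | 36.7 | 2.027 | 5.81 | 76% |

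Pooled tests (58 df) change the shifts by at most 0.04°.

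**Two-week flexion.** The document prints "Flexion at two weeks for the intervention group was 133.80 ± 6.79 and for the control group it was 131.17 ± 2.20" with p = 0.001. From those figures t = 2.63 / 1.303 = 2.02, with p = 0.048 pooled and 0.051 Welch. No bias is needed to make this result uncertain. The visible text names no test, so another analysis may lie behind the printed value. Either way the mismatch concerns the reported p-value and says nothing about who read the goniometer.

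**What a change could achieve.** In the completed trial no reading can be retaken blind. In a repeat, the sure route is a second assessor for 60 women × 2 visits = 120 home visits. Reassigning tasks between existing staff would cost less, but it assumes that the PI and the researcher are two people, which is not stated. It would also need someone other than the visitor to hold the result of the coin flip, and the text does not say who flipped the coin.

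**The case for a change.** The best argument for acting is that the reader is left unable to judge. The PI wrote the material, explained the study including the weekly calls for one arm, and was announced as the home assessor, so knowledge of group is a reasonable inference. Tipping points address significance only: a shift well short of 3° would leave p-values small and still inflate the estimated effects. A few sentences of disclosure cost almost nothing.

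Much of this stands. The inference is plausible, and smaller shifts could inflate the estimates. The documents give no goniometer error, so they cannot show that bias was negligible any more than that it was large. The report would be clearer if it named the follow-up assessor and said whether that person knew the arm; if so, readers should be told that the ROM differences rest on unmasked readings.

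That is a request to complete a description, however, and authors can meet it from what they already know. It alters no design feature, analysis or estimate. Nor does the calculation give a firm order of robustness among the five clear results. In degrees, four-week abduction (5.81°) looks safer than four-week extension (3.14°), but extension has the larger t (8.99 against 8.51) and the larger share of its difference (78% against 76%).

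**Conclusion.** The concern does not call for a change to the plan. It identifies a gap in the description: the visible text does not say whether the week-2 and week-4 assessor knew the group. It does not show that the assessor knew, and the unseen figure may settle the point. With data collection finished, the gap can be closed only by a statement in the report. Masking in a repeat would be a resource decision of up to 120 additional-assessor visits, and the self-reported QoL-BC would remain unmasked.

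If assessment was in fact open, five of the six ROM results would keep significance under any constant shift smaller than 3.04° to 6.41°, depending on the result. This rests on three assumptions: the ± values are SDs, 30 women per arm were analysed, and the bias is constant and favours the trained arm. Two-week flexion is uncertain on its own printed figures, and its printed p-value should be considered separately from masking.

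### Week 2 and week 4 comparisons: no baseline adjustment, test, between-group difference or confidence interval is evident in the available text, although baselines were collected in both arms

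*Combined protocol and SAP*

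**What the plan says.** The section on the intervention places the baseline assessment on the day before surgery, when both "groups completed the QoL-BC survey and shoulder ROM was measured using the goniometer". It also states "All patients completed the study". A baseline and two follow-up values should therefore exist for every woman and every outcome. The Protocol section says that women were "randomly assigned to one of two groups by flipping a coin", 30 to each arm, and describes no stratification.

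The Results paragraph on shoulder ROM says "While the shoulder ROM scores were not significantly different between groups prior to surgery, there were significant differences at the second and fourth weeks" and cites Table 2. The paragraph on QoL-BC says "There were no significant differences between groups at baseline on the QoL survey with both groups having low QoL scores", and then that "there were significant differences between groups at two and four weeks after surgery on the four subscales (Table 3").

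The follow-up results are 14 contrasts: three movements and four subscales, each at two weeks and four weeks. Each is given as two arm means with ± values and a p-value. Twelve p-values are printed as below 0.001. The two exact ones are two-week flexion, "133.80 ± 6.79 and for the control group it was 131.17 ± 2.20 , $p = 0.001", and two-week physical well-being, "58.37 ± 6.16 versus 50.23 ± 7.78 , $p = 0.001". The available text names no test, model or covariate and gives no between-group difference or confidence interval.

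**The concern.** The text offers non-significance before surgery as the evidence of comparability and then compares the arms at follow-up. With 30 per arm, a non-significant baseline test still allows a sizeable chance imbalance, and simple coin-flip allocation does not limit it. Non-significance is not a reason to leave the baseline out of the model.

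Two things are at stake. The first is modest: some precision, and an estimate that accounts for whatever imbalance occurred. The second is checkability. Because the method is not named, a reader cannot tell what the p-values test, and the only two that can be compared closely with the printed means do not agree with a plain t-test.

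**Working it through.** **Inputs.** n = 30 per arm (Protocol section); no dropout (section on the intervention); arm means and ± values (Results). Assumed, because the text does not say: ± is an SD, tests are two-sided at 0.05, r is the baseline-outcome correlation, and d is the baseline imbalance in SD units (intervention minus control).

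**1. The two exact p-values, unadjusted.** With 58 df, p = 0.001 needs |t| = 3.47.

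- Two-week flexion: difference 133.80 − 131.17 = 2.63. Pooled SD = √[(6.79² + 2.20²)/2] = 5.05. SE = 5.05 × √(2/30) = 1.303. t = 2.02, p = 0.048; Welch (35.0 df) p = 0.051. The printed value would need an SE of 2.63/3.47 = 0.76. If ± were a standard error, t would be 2.63/√(6.79² + 2.20²) = 0.37, further away still.
- Two-week physical well-being: difference 58.37 − 50.23 = 8.14. Pooled SD 7.02, SE 1.812, t = 4.49, p = 0.00003 (0.00004 Welch). The printed value would need an SE of 8.14/3.47 = 2.35.

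The two miss in opposite directions. The other 12 contrasts agree with p < 0.001 under both tests.

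**2. Unadjusted differences (Welch 95% CI).**

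| Outcome | Week 2 | Week 4 |
|---|---|---|
| Flexion | 2.63 (−0.02 to 5.28) | 8.05 (6.41 to 9.69) |
| Extension | 4.04 (3.04 to 5.04) | 4.04 (3.14 to 4.94) |
| Abduction | 4.93 (3.17 to 6.69) | 7.63 (5.81 to 9.45) |
| Physical | 8.14 (4.51 to 11.77) | 11.70 (7.53 to 15.87) |
| Psychological | 19.40 (13.09 to 25.71) | 23.83 (13.06 to 34.60) |
| Social | 14.27 (10.29 to 18.25) | 12.00 (8.29 to 15.71) |
| Spiritual | 6.17 (3.44 to 8.90) | 7.40 (5.66 to 9.14) |

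**3. What baseline non-significance leaves open.** Limit = t(0.975, 58) × √(2/30) = 2.002 × 0.258 = 0.517 SD. Random allocation exceeds this about 5% of the time; one SE of imbalance is 0.258 SD.

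**4. Precision gained.** Proportional cut in SE = 1 − √(1 − r²): 0.046 at r = 0.3 and 0.134 at r = 0.5.

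**5. Sensitivity with a common slope and equal baseline SDs.** Slope b = r × pooled SD; estimate = difference − b × d; arm residual variance v = SD² − b²; variance = v₁/30 + v₂/30 + d² × mean(v₁, v₂)/58; Satterthwaite df. Since v cannot be negative, r cannot exceed smaller SD/pooled SD. For two-week flexion that cap is 2.20/5.05 = 0.44, so the SE cut is at most about 10% in this model.

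| Two-week flexion: r | d | Estimate | p |
|---|---|---|---|
| 0 | 0 | 2.63 | 0.051 |
| 0.3 | 0 | 2.63 | 0.042 |
| 0.435 | 0 | 2.63 | 0.033 |
| 0.3 | +0.258 | 2.24 | 0.083 |
| 0.3 | −0.258 | 3.02 | 0.022 |
| 0.3 | +0.517 | 1.85 | 0.160 |
| 0.3 | −0.517 | 3.41 | 0.012 |

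For the other 13 contrasts, with r up to the smaller of its cap and 0.7 and d to ±0.517, the largest p is about 0.0003 (pooled variance) or 0.0005 (arm-specific variances), in both cases for psychological well-being at week 4.

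**6. Could adjustment explain the printed 0.001?** With a common slope and r up to 0.435, the smallest flexion p is 0.003 pooled or 0.004 arm-specific, so it is not reproduced. If each arm has its own slope, the 0.44 cap no longer applies. At the mean of the two arms' baselines, estimate = 2.63 − d × r × (6.79 + 2.20)/2, and variance = Σ SD²(1 − r²)[1/30 + (d/2)²/29].

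- r = 0.6, d = −0.517: 2.63 + 1.39 = 4.02, SE 1.08, p about 0.0007 (35 df).
- r = 0.7, d = −0.258: 2.63 + 0.81 = 3.44, SE 0.94, p about 0.0008 (35 df).

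Both round to 0.001. For physical well-being at week 2, the largest p on the step 5 grid is 0.0003, so its printed value is not reproduced there.

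**The case against.** The strongest reply is that little depends on this. Randomisation makes the unadjusted comparison valid, and its standard error already allows for chance imbalance. That stands: the case for adjustment is precision and an account of the imbalance that occurred, not removal of bias.

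Second, Tables 2 and 3 are cited but were not available; they may hold baseline summaries, test names, differences or intervals. That also stands. A reader might infer that the analysis was unadjusted. The text does not support this: adjustment is not evident, which is weaker than absent.

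Third, the differences and intervals can be derived from the printed means, as in step 2, and 13 of them lie far from zero. For those contrasts the gap is largely one of presentation. The derivation does, however, require the reader to assume that ± is an SD.

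Fourth, the p-value mismatches are a reporting matter distinct from baseline adjustment. A rank test, an adjusted model or a typing slip could lie behind either. This is fair, and the mismatches should not add weight to the case for adjustment. They do show why the method must be named.

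A reader might also infer that no adjusted model could give the printed flexion value. Step 6 shows that this depends on a common slope, which is doubtful when the two-week SDs differ by a factor of 3.1. The arm-specific scenarios need favourable assumptions, and nothing shows that they occurred, but they cannot be ruled out.

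**Conclusion.** The concern holds as a modest, inexpensive improvement in analysis and reporting. Baselines were collected with no dropout reported, and the available text shows no use of them beyond statements of non-significance. It names no test and gives no effect estimate with an interval.

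Adjustment would reduce the standard error by roughly 5% to 13% for correlations of 0.3 to 0.5. These correlations are assumed, and the lower caps in step 5 limit the gain for some outcomes if the slope is common. Thirteen of the 14 conclusions would not change under the correlations and imbalances examined. Two-week flexion is the exception: it sits at the 0.05 border unadjusted, and at r = 0.3 it runs from 1.85° (p = 0.16) to 3.41° (p = 0.01) across imbalances that would pass as non-significant.

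The documents do not support a reading that the trial's results are biased or that its main findings fall. Nor can it be determined, without the baseline data, whether an adjusted model accounts for the printed flexion p-value. All figures take ± as SD; confidence is medium because the tables were not seen.

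**What to change.** 1. State the test or model behind the printed p-values, and say what ± denotes.
2. For each movement and each subscale, estimate the week 2 and week 4 group differences by ANCOVA on that outcome's own baseline. Alternatively, use one repeated-measures model with baseline, group, week and group-by-week terms.
3. Use heteroscedasticity-robust or arm-specific variances, since the arm SDs differ by factors of 1.6 to 3.1 for ROM and 1.2 to 2.1 for QoL-BC.
4. Report adjusted differences with 95% confidence intervals. If Tables 2 and 3 do not already do so, show baseline means and SDs by arm in place of significance tests.
5. Correct or explain the two printed values of 0.001 against the method actually used.

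The cost is a small re-analysis of data already collected, with no new measurements. Because the results are known, a model chosen now is post hoc unless it was pre-specified, and must be labelled so.

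### The printed p = 0.001 for two-week flexion does not follow by t-test from the printed means and unequal SDs (pooled p = 0.048, Welch p = 0.051), and no test is named

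*Combined protocol and SAP*

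**What the plan says.** All of this is in the combined protocol and SAP.

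- **Protocol section, numbers:** "Thirty women ended up in the intervention group and 30 in the control group".
- **The intervention section, follow-up:** "All patients completed the study". Each two-week and four-week mean should therefore rest on 30 women.
- **Results, shoulder range of motion scores, overall claim:** "there were significant differences at the second and fourth weeks after surgery".
- **Same section, two-week flexion:** "Flexion at two weeks for the intervention group was 133.80 ± 6.79 and for the control group it was 131.17 ± 2.20", with p = 0.001.
- **Same section, four-week flexion:** "167.97 ± 4.09 for the intervention group and 159.92 ± 1.73 for the control group", with p < 0.001.
- **Same section, abduction:** "at two weeks 143.50 ± 4.42 versus 138.57 ± 1.78", with p < 0.001.

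Extension is reported in the same format. The text gives no confidence interval, range or median. It names no test or significance level, does not define the ± figure, and does not comment on the unequal spreads. Table 2 is cited there but is not reproduced in the text, so a footnote in it may answer some of this.

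**The concern.** The two arms are the same size, yet the intervention arm is more variable in every range-of-motion row, and about three times as variable for two-week flexion. That row also has the smallest mean difference of the six. A small difference with one very wide arm should give weak evidence, but the printed p-value is strong. The figures in that sentence do not appear to belong together.

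What is at stake is one claim: that flexion already differs clearly between the arms at two weeks. If the printed means and SDs are right and a t-test was meant, the evidence is borderline and the interval just includes zero. If the p-value is right and a t-test was meant, then a mean or an SD is wrong. A reader cannot tell which without the test's name and a source check.

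**Working it through.** **Inputs.** n = 30 per arm (Protocol section), with no dropout (The intervention section). Means and ± values come from the shoulder range of motion results. Two assumptions are mine because the text is silent: ± is the SD, and tests are two-sided.

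**Step 1: try to reproduce p = 0.001 for two-week flexion.**

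- Difference = 133.80 − 131.17 = 2.63°.
- SE = √[(6.79² + 2.20²)/30] = √[(46.10 + 4.84)/30] = 1.303°.
- t = 2.63/1.303 = 2.02. With equal arm sizes this is the same for the pooled and Welch tests.
- Pooled, 58 df: p = 0.048.
- Welch df = (46.10 + 4.84)² / [(46.10² + 4.84²)/29] = 35.0, giving p = 0.051 (one-sided 0.026).
- Welch 95% CI = 2.63 ± 2.03 × 1.303 = −0.02° to 5.28°.

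None of these gives 0.001. If ± were a standard error, t would be 2.63/√(6.79² + 2.20²) = 0.37, which is further away.

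**Step 2: how far off are the printed figures?** On 58 df, p = 0.001 needs t = 3.47.

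- Holding the difference and the control SD fixed, the pooled SD must be 2.63/(3.47 × √(2/30)) = 2.94. The intervention SD is then √(2 × 2.94² − 2.20²) ≈ 3.5, not 6.79.
- Any p that rounds to 0.001 (0.0005 to 0.0015) needs an intervention SD between 3.2 and 3.7. With both printed SDs kept, it needs a difference between 4.3° and 4.8°.

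Rounding of the printed values cannot cover that gap.

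**Step 3: all six rows.** SD ratio is intervention over control.

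| Motion, week | Intervention | Control | SD ratio | Difference (Welch 95% CI) | Welch p |
|---|---|---|---|---|---|
| Flexion, 2 | 133.80 ± 6.79 | 131.17 ± 2.20 | 3.09 | 2.63 (−0.02 to 5.28) | 0.051 |
| Flexion, 4 | 167.97 ± 4.09 | 159.92 ± 1.73 | 2.36 | 8.05 (6.41 to 9.69) | 3.1e-12 |
| Extension, 2 | 42.77 ± 2.30 | 38.73 ± 1.46 | 1.58 | 4.04 (3.04 to 5.04) | 1.2e-10 |
| Extension, 4 | 53.07 ± 2.12 | 49.03 ± 1.25 | 1.70 | 4.04 (3.14 to 4.94) | 8.8e-12 |
| Abduction, 2 | 143.50 ± 4.42 | 138.57 ± 1.78 | 2.48 | 4.93 (3.17 to 6.69) | 1.6e-6 |
| Abduction, 4 | 167.03 ± 4.61 | 159.40 ± 1.69 | 2.73 | 7.63 (5.81 to 9.45) | 3.3e-10 |

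The variance ratio for two-week flexion is 3.086² = 9.5 (F test on 29 and 29 df, p = 3.4e-8, normality assumed). Five rows agree with their printed p < 0.001. Only two-week flexion does not.

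**Step 4: could one reading be responsible?** Suppose the other 29 intervention women had the control SD of 2.20. One reading would then have to lie √[(29 × 6.79² − 28 × 2.20²) × 30/29] = 35.3° from their mean. It would move the arm mean by 35.3/30 = 1.18°. Without it the difference would be 3.81° (low reading) or 1.45° (high reading). This is an illustration, but it shows that a single sheet could matter in either direction.

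**The case against.** **A different analysis may explain the p-value.** The p-value need not come from a t-test. A rank test responds to the ordering of values and is less affected by a few extreme ones, and a baseline-adjusted analysis would use a different error term. In simulated normal data with the printed means and SDs, a Mann–Whitney test reached p ≤ 0.0015 in about 10% of runs, so this is possible though not the expected result. The only other p printed as equal to 0.001, for two-week physical well-being (58.37 ± 6.16 versus 50.23 ± 7.78), is about 0.00003 by pooled t-test. That is a mild hint of another test or of loose rounding. This objection stands, so the discrepancy cannot be called an error in the p-value. It does not remove the need to name the test.

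**Unequal spread is not a defect in itself.** With equal arms, the t statistic is the same pooled or Welch, and five of six conclusions do not change. The pattern is also not general: in four of the eight quality-of-life rows the control arm has the larger SD. This stands too, and limits the point to one row.

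**A reader might infer more from the wide spread than it supports.** A normal model puts Φ(−2.63/6.79) = 35% of intervention women below the control mean, which could be read as a third of them doing no better. That needs normality, which the document does not establish; mean and SD alone limit the share only to at most 1/(1 + (2.63/6.79)²) = 87%. Under the same model 50% of controls lie below their own mean, so 35% is consistent with a modest average benefit.

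**Conclusion.** The point holds for two-week flexion. On the printed means and SDs, a t-test gives p = 0.048 (pooled) or 0.051 (Welch), with a difference of 2.63° and a 95% CI of −0.02° to 5.28°. The stated p = 0.001 needs another explanation: a wrong SD or mean, an extreme reading, a wrong p-value, or an unnamed analysis. The result rests on ± being the SD, 30 women measured per arm, and two-sided testing. The wider intervention spread in all six rows is a fact of the printed figures, but it changes no conclusion in the other five.

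Two further readings are tempting and unsupported.

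- **Some women were made worse.** The spread might suggest this, but values at one time point without individual change scores cannot show it. Large gains in a few women, variable adherence, unequal baseline spread, an outlier or a misprint could all produce it.
- **Some women were still under the early flexion limit** ("Shoulder flexion was limited to 90° of active assisted", in The intervention section). With n = 30 and SD 6.79, no reading can be further than (29/√30) × 6.79 = 35.95° from the mean. None can therefore be below about 97.8°, and no woman measured at 90° or less.

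Nor does the text claim that every woman benefited, so there is no such claim to correct.

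**What to change.** 1. Check the two-week flexion SD and the extreme intervention-arm readings against the source sheets.
2. Name the test behind each range-of-motion p-value, say whether it is two-sided and adjusted for baseline, and state that ± is the SD if it is.
3. Report each difference with a 95% CI from an analysis that allows arm-specific variances (Welch or heteroscedasticity-robust).
4. Correct the two-week flexion SD or p-value, whichever proves wrong. If a rank or adjusted analysis produced 0.001, say so and give the Welch result beside it.
5. Until that is done, do not describe two-week flexion as a clearly significant difference.

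The cost is about a day of re-analysis at most, from data already held, with no new patients or visits. The downside is that the two-week flexion claim may become less favourable. The other five range-of-motion differences stand.

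### The two-week flexion p = 0.001 does not follow from the means, SDs and group sizes printed with it; an unadjusted comparison of means gives p of about 0.05

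*Combined protocol and SAP*

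**What the plan says.** The Results section on shoulder range of motion gives flexion at two weeks, intervention against control, as "133.80 ± 6.79 and for the control group it was 131.17 ± 2.20 , $p = 0.001". The row supports a general statement about range of motion: "there were significant differences at the second and fourth weeks after surgery (Table 2").

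The group sizes are in the Protocol section: "Thirty women ended up in the intervention group and 30 in the control group". The section on the intervention adds "All patients completed the study", so 30 women per arm apply at week two.

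The supplied text does not name the test, say whether it was adjusted for baseline, or say whether ± is an SD or a standard error. Tables 2 and 3 are cited, but their contents are not in the supplied text.

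**The concern.** A mean, an SD and a group size in each arm fix the result of an unadjusted comparison of means. Here the difference is small against the intervention SD, and the p-value looks far too strong for it.

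A p of 0.001 presents two-week flexion as strong evidence. If the printed summaries are right and the test was unadjusted, the lower confidence limit is about zero, and whether the row passes 0.05 depends on which t-test is used. A reader cannot tell whether to trust the p-value or the summaries.

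**Working it through.** **Inputs.** Intervention 133.80, SD 6.79; control 131.17, SD 2.20 (Results, shoulder range of motion). n = 30 per arm (Protocol), with no dropout (The intervention). Reading ± as SD is an assumption.

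**Attempt to reproduce p = 0.001**

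- Difference: 133.80 − 131.17 = 2.63°.
- Standard error: √[(6.79² + 2.20²)/30] = √[(46.10 + 4.84)/30] = √1.698 = 1.303.
- t = 2.63/1.303 = 2.018.
- Pooled, 58 df: p = 0.048. 95% CI 2.63 ± 2.002 × 1.303 = 0.02 to 5.24.
- Welch, 35.0 df: p = 0.051. 95% CI 2.63 ± 2.030 × 1.303 = -0.02 to 5.28.

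The printed figure is not reproduced. The variance ratio is 46.10/4.84 = 9.5, which favours Welch.

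**Simple explanations**

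- *Rounding.* Varying the inputs within their last digit keeps p within 0.047 to 0.049 (pooled) or 0.050 to 0.052 (Welch).
- *± as standard error.* t = 2.63/√(6.79² + 2.20²) = 2.63/7.14 = 0.37, p = 0.71.
- *Normal approximation or one-sided test.* 0.044, and 0.024 to 0.026.
- *Paired t-test, wrongly applied.* From 0.053 at correlation 0 to 0.004 at correlation 1.

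**How far an input would have to move** for p to fall below 0.0015 and so round to 0.001, with the other inputs fixed:

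| Input | Printed | Needed (pooled) | Needed (Welch) |
|---|---|---|---|
| Women per arm | 30 | 78 | 79 |
| Intervention SD | 6.79 | 3.72 | 3.66 |
| Difference | 2.63° | 4.34° | 4.49° |

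As a plausibility check on the SD, four-week flexion is printed as "167.97 ± 4.09 for the intervention group and 159.92 ± 1.73 for the control group, $p < 0.001". Putting that smaller intervention SD, 4.09, in place of 6.79 still gives p = 0.0030 (pooled) or 0.0033 (Welch).

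**The other 13 comparisons, same method**

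| Row | Printed p | Pooled | Welch |
|---|---|---|---|
| Two-week extension, "42.77 ± 2.30 versus 38.73 ± 1.46 , $p < 0.001" | < 0.001 | 3.8e-11 | 1.2e-10 |
| Two-week abduction, "143.50 ± 4.42 versus 138.57 ± 1.78 , $p < 0.001" | < 0.001 | 4.8e-7 | 1.6e-6 |
| Four-week flexion | < 0.001 | 4.0e-14 | 3.1e-12 |
| Two-week physical well-being, "at two weeks, 58.37 ± 6.16 versus 50.23 ± 7.78 , $p = 0.001" | 0.001 | 3.4e-5 | 3.6e-5 |

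The largest recomputed p among the 12 rows printed as below 0.001 is 6.0e-5 (four-week psychological well-being, Welch), so all 12 are consistent with a t-test. Being inequalities, they cannot show that a t-test was used. Physical well-being, the only other exact p, also fails to reproduce, but in the conservative direction.

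**Could an unnamed method give 0.001?** The inputs here are assumptions, because the text gives neither baseline values nor individual data.

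- *Baseline-adjusted model* (57 df, common baseline-to-week-two correlation r, equal baseline means): p = 0.025 at r = 0.5, 0.0069 at r = 0.7, and about 0.0015 at r = 0.80.
- *Rank test*, simulated with 4,000 samples per shape, scaled to the printed means and SDs, control values normal:

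| Assumed intervention shape | Median p | Share below 0.0015 |
|---|---|---|
| Normal | 0.058 | 0.1% |
| Right-skewed exponential | 0.38 | 0% |
| Left-skewed exponential | 0.0024 | 39% |
| 29 normal values, one about 25° below | 0.0049 | 16% |
| 29 normal values, one about 30° below | 0.0005 | 84% |

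Either method could produce 0.001 in some circumstances. Nothing in the supplied text shows that either was used.

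**The case against.** The strongest reply is that the benchmark is assumed. No test is named, and the only two exact p-values miss an unadjusted t-test in opposite directions: flexion is printed stronger and physical well-being weaker. A different, unnamed test could produce that pattern, though so could typing errors. This stands, and it is why the conclusion must stay conditional.

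The equal-baseline calculation may also make adjustment look harder than it was. The document says only that baseline range of motion did not differ significantly. Suppose the intervention arm started lower, with imbalance in units of the pooled week-two SD. An imbalance of 0.2 SD with r = 0.7 gives p = 0.0008 (baseline p = 0.44). With r = 0.6, 0.3 SD gives 0.0015 (baseline p = 0.25) and 0.4 SD gives 0.0007 (baseline p = 0.13). Imbalance the other way would weaken the result. Adjustment is therefore a live explanation, but if it is the true one the report should say so and give the adjusted estimate.

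A single wrong digit would also suffice. An intervention mean of 135.80 instead of 133.80 gives p = 0.0008 (pooled) or 0.0011 (Welch). The slip could be the authors' or could have arisen when the PDF was read, and Table 2 is not available to settle it. This too stands as a caveat, and only a check of the row can resolve it.

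Finally, the impact is small: one row of 14, with pooled p still under 0.05. That limits the consequence but does not remove the disagreement between the p-value and the figures beside it.

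**Conclusion.** The concern holds. Under an unadjusted comparison of means, with 30 per arm and ± as SD, the two-week flexion summaries give p of about 0.05 against a printed 0.001, roughly a fifty-fold discrepancy. Confidence in that conditional statement is high. The documents do not show whether the fault lies in a mean, an SD, the p-value or an unreported choice of method.

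If the summaries are right and the test was unadjusted, the evidence for two-week flexion is borderline and is overstated as printed. Nothing beyond this row is affected: two-week extension and abduction and all the four-week range-of-motion results remain firm, and the quality-of-life conclusions do not change.

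**What to change.** Check the two-week flexion row against source data, and state in one sentence which test produced the 14 comparisons and what ± denotes. Then:

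1. If a mean, SD or p-value was mistyped, correct it.
2. If the summaries stand and the test was an unadjusted comparison of means, print p of about 0.05 with the 2.63° difference and its 95% CI, describe two-week flexion as borderline, and rest the firm two-week range-of-motion claim on extension and abduction.
3. If a baseline-adjusted or rank analysis gave 0.001, name it and report its own estimate and interval.

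Check the two-week physical well-being p-value at the same time; its conclusion will not change.

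The cost is low: two p-values checked, one sentence added and, depending on the outcome, one row and the wording of one claim corrected. No new data are needed.
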